10.1.7. Administration

Vials with the dissolved drug are stored refrigerated. Each vial should be mixed with a gentle swirling motion. As with all protein based products, avoid vigorous shaking. The solution must be yellow and translucent. The solution must not be used unless it is translucent and without visible particulate matter.

The aliquot is calculated in $\mu\text{eq}/\text{kg}$ dose \times patient weight in kg. (All patient doses are calculated in $\mu\text{eq}/\text{kg}$ body weight). On the day of administration, the appropriate volume is withdrawn from one or more vials and then diluted into 250 ml of either 5% or 10% dextrose (per discretion of Principal Investigator) for infusion. It is infused over a period of 90 minutes.

10.1.8. Risks

The primary side effect predicted in adults receiving 765IGF-MTX is low blood sugar immediately after receiving the drug. This will be treated by intravenous administration of either 5% or 10% dextrose (per discretion of Principal Investigator) or by oral administration of sugar.

The following toxicities are predicted in adults receiving methotrexate: Immediate side effects include allergic reactions associated with low blood pressure, shortness of breath, hypotension, , back pain and hives. These will be treated with medications, fluids and oxygen. If symptoms persist, the patient may have to be hospitalized for further treatment.

Other adverse events that have been observed with 765IGF-MTX administration have been nausea, syncope, tachycardia, fever and chills, seizure, and abdominal cramps. These have been observed during the infusion or within 3 hours after infusion.

Delayed toxicities of methotrexate which occur within hours to days include skin rashes, diarrhea, fever, anorexia, nausea, vomiting, mouth sores, fatigue, malaise, myalgias, arthralgias, chills, high blood sugar level. These will be treated with medications as needed. Work up for infections will be conducted as needed.

Possible late toxicities include abnormal liver function tests. These effects occur several days to a week after treatment. See section 10.1.9 **Warnings and Precautions**.

Rare toxic effects of methotrexate include encephalopathy, sensory changes, kidney problems, and lung problems. See section 10.1.9 **Warnings and Precautions**.

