7.1. Study Drug Administration

After Cycle #1 a new treatment cycle will be initiated when all of the following conditions are met:

- Non-hematologic treatment related toxicities have improved to grade 1 or resolved (CTCAE v.4.0)
- Platelets $> 10 \times 10^9/L$

Refer to section 7.3 for guidelines for dose modifications based on treatment-related delays and toxicities of the previous cycle.

7.1.1. 765IGF-Methotrexate Administration

765IGF-MTX will be given at the assigned dose as a 1.5 hour IV infusion in 250 ml of 5% dextrose on days 1, 8, and 15 of a four-week treatment cycle. Every 4 week period will be considered one treatment cycle. Subsequent cycles must meet the criteria found in section 7.3.1 and may begin 1 day earlier to accommodate scheduling issues, or up to 4 weeks later if a patient needs this time to recover to meet criteria for start of a new cycle as specified in section 7.2.1. At the investigator's discretion, the study drug may be administered in 10% dextrose rather than 5% dextrose if it is believed necessary to prevent or control hypoglycemia.

Pre-medication

None is required, but can be utilized per clinician discretion. The program of predication below has been used in the prior solid tumor phase I with some of the later enrolled patients to prevent nausea and an allergic reaction. Nausea during infusion was seen in a few patients and a possible allergic reaction to the drug was seen in one patient.

Zofran 8mg PO
Benadryl 50mg PO
Tylenol 650mg PO
Hydrocortisone 100mg IV push
D5 .45 normal saline 100cc/hr to start with premeds

Monitoring

Vital signs including blood pressure, pulse, temperature, respirations, and pulse oximetry, and blood glucose will be measured immediately before the infusion and immediately after completion of the infusion in all patients during all cycles. IGF-MTX causes hypoglycemia at higher dose levels, so it is important to monitor blood glucose levels. During the first 28-day cycle, patients will be monitored for blood glucose on infusion days for a total of 3.5 hours. Vital signs listed above will be monitored per the following table:

Monitoring interval	
Immediately before infusion	All vitals
To Hour 1.5 (during infusion)	Glucose only, every 15 min
Hour 1.5	All vitals
Hours 1.5-3.5	Glucose only, every 30 min

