The patients will be provided with a home blood glucose monitoring device and instructed to measure and record blood glucose at 7 hours (\pm 2 hours) and 24 hours (\pm 6 hours) after the start of the infusion. The same device will be used to monitor blood glucose at the clinic during the 3.5 hour monitoring.

On all subsequent cycles that patients are on treatment (i.e., cycle 2 and beyond), those patients that did not experience a severe adverse event during the infusion and 3.5-hr post-infusion period in cycle 1 will be monitored for a total of 2.5 hours on infusion days (i.e., during the 1.5 hour infusion and one hour after termination of the infusion). Vital signs listed above will be monitored per the following table:

Monitoring interval	
Immediately before infusion	All vitals
To Hour 1.5 (during infusion)	Glucose only, every 15 min
Hour 1.5	All vitals
Hours 1.5-2.5	Glucose only, every 30 min

The patients will be instructed to measure and record blood glucose at 7 hours (\pm 2 hours) and 24 hours (\pm 6 hours) after the start of the infusion for each dose.

Patients will be closely monitored for toxicities. Strict I/O will be measured during patient stay both in the ambulatory and inpatient setting (per unit protocol).

Supportive Measures: See also section 7.7

Hypoglycemia will be treated with oral glucose or if necessary IV glucose to maintain blood glucose levels above 50 mg/dl. Acetaminophen for fevers, meperidine for chills, anti-emetics for nausea and vomiting, normal saline or furosemide to maintain fluid balance/blood pressure/pulmonary function, electrolyte replacement, albumin to maintain serum albumin at 3 g/dL or greater. Anaphylactoid reactions will be treated with 100 mg methylprednisolone IV, diphenhydramine 25 mg IV, or 0.3 cc epinephrine (1:1000) IV and transfer to an ICU setting for monitoring. Refer to section 7.2.1. regarding management of Allergic Reaction/Hypersensitivity reactions.

Precautions

Patients should not drive, operate dangerous tools or machinery, or engage in any other potentially hazardous activity that requires full alertness and coordination if they experience sedation while enrolled in this study.

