7.7. Management of Clinical Events and Supportive Care Guidelines

Optimal patient care is to be provided to all patients.

Patients should receive full supportive care during the study, including transfusion of blood and blood products, treatment with antibiotics, analgesics, or erythropoietin, when appropriate.

Although acetaminophen at doses of ≤ 2 grams/day is permitted, it should be used with caution in patients with impaired liver function.

Patients with significant third spacing (anasarca, symptomatic pleural effusions, symptomatic ascites) should be monitored closely.

Infusion of IGF-methotrexate for 1.5 hours and follow up observation for an additional 1-2 hours (see section 7.1.1. for further details on duration of follow up observation) will be performed in monitored room with available sealed cart with Diazepam 2 mg vials for immediate intravenous infusion in case of seizures. The following protocol will be in place in case of this drug toxicity:

- Call physician on service.
- Start BLS SPECIFIC CARE:
 - Administer oxygen (high flow if neurological deficits or altered mental status)
 - Place the patient in recovery position, and prevent accidental harm.
 - Anticipate brief combativeness or agitation in post-ictal phase.
- Start ALS SPECIFIC CARE:
 - Anticonvulsant Therapy
 - Diazepam (Valium): IV: 2-10 mg, every 5-10 minutes as needed (max of 20 mg), if status epilepticus start phenytoin load 20 mg/kg.

Once the situation is resolved, the duration of further monitoring will be at the discretion of the study physician.

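### The driving precaution applies only after sedation, yet 1 to 2 h of the protocol's own 3 h post-infusion event window, which includes syncope and seizure, falls after release

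*Combined protocol and SAP*

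**What the plan says.** - **Event window.** Section 10.1.8 names six kinds of event observed with 765IGF-MTX: syncope, seizure, tachycardia, nausea, abdominal cramps, and fever with chills. It gives one timing for all of them: "These have been observed during the infusion or within 3 hours after infusion". No event is timed separately.
- **Cycle 1 observation.** Section 7.1.1 sets a 1.5 h infusion and states that "patients will be monitored for blood glucose on infusion days for a total of 3.5 hours". The table there ends at hour 3.5; after hour 1.5 the only scheduled measurement is glucose.
- **Cycle 2 onward.** Patients with no severe adverse event "during the infusion and 3.5-hr post-infusion period in cycle 1 will be monitored for a total of 2.5 hours on infusion days", which the text explains as the infusion plus "one hour after termination of the infusion".
- **Monitored room.** Section 7.7 describes "follow up observation for an additional 1-2 hours" in a room with diazepam at hand for seizures.
- **Driving and hazardous activity.** The precaution in 7.1.1 applies only to patients "if they experience sedation while enrolled in this study".
- **After release.** Patients are "instructed to measure and record blood glucose at 7 hours" and again at 24 hours, both from the start of the infusion, with a home device.

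**The concern.** The protocol treats seizure as a foreseeable infusion-day risk: it excludes anyone with a prior seizure (5.2.12) and keeps an anticonvulsant in the room (7.7). Yet required observation stops before the protocol's own event window closes. The one instruction that could protect a patient who has left, the driving precaution, is triggered by sedation. Sedation is not on the 10.1.8 list of observed events, and a faint or seizure need not be preceded by it. On the protocol text, a patient who feels well may therefore drive away inside the stated window. At stake is the safety of the patient and of others on the road, not the analysis.

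A second, smaller matter is the rule that decides who gets the shorter observation. It refers to a post-infusion period of 3.5 h, whereas the schedule provides 3.5 h in total, counted from the start of the infusion.

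**Working it through.** The check is subtraction on one clock, set to zero at the start of the infusion.

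**Inputs.** Infusion 1.5 h; total observation 3.5 h (cycle 1) and 2.5 h (cycle 2 on, stepped down); home glucose check at 7 ± 2 h from the start (all 7.1.1). Event window to 3 h after infusion (10.1.8).

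**Step 1: the plan's own figure.** Post-infusion observation = total − infusion.
- Cycle 1: 3.5 − 1.5 = 2.0 h.
- Cycle 2 on: 2.5 − 1.5 = 1.0 h.

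This reproduces the 1 to 2 hours in section 7.7, so the schedule itself is clear.

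**Step 2: against the stated window.** The window closes at 1.5 + 3.0 = 4.5 h.

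| | Observation ends | Window closes | Window left after release |
|---|---|---|---|
| Cycle 1 | 3.5 h | 4.5 h | 4.5 − 3.5 = 1.0 h |
| Cycle 2 on, stepped down | 2.5 h | 4.5 h | 4.5 − 2.5 = 2.0 h |

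**Step 3: does anything else cover that time?**
- The home glucose check falls between 7 − 2 = 5 h and 7 + 2 = 9 h. The earliest is 5 − 4.5 = 0.5 h after the window closes, and it measures glucose only.
- An ECG at 3 h after infusion and later blood draws (8.2, 9.3) keep some patients in contact. These are only the pharmacokinetic patients at the MTD, on days 1 and 15 of cycle 1.
- The extended monitoring after a seizure in 7.7 follows an event managed on site.
- The exclusion of prior seizures does not address syncope or a first seizure.

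**Step 4: the other reading of 3 hours.** If the 3 h ran from the start of the infusion, which is less natural given the wording, cycle 1 would be covered (3.5 > 3). Cycle 2 on would fall 3 − 2.5 = 0.5 h short. The sedation-only precaution would still miss that half hour.

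**Step 5: the step-down phrase.** Read literally, 3.5 h after the infusion ends at 1.5 + 3.5 = 5.0 h. That is 5.0 − 3.5 = 1.5 h beyond scheduled observation, and 5.0 − 4.5 = 0.5 h beyond the close of the event window. The phrase does not match the table, but a severe event in that extra time already blocks step-down.

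**The case against.** The strongest reply is that the 3 h limit is the outer bound of a pooled list. It could come from nausea or cramps, and every syncope and seizure could have occurred during the infusion. That is right. A reader might infer that patients have fainted or seized after the time at which this protocol would release them; the documents do not show it. Some background text before section 1.3 was not available and may hold timing detail, so no missing rationale is alleged.

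The schedule also has a visible logic. Section 10.1.8 gives low blood sugar immediately after dosing as the main predicted effect. Observation is built around glucose, is longest in cycle 1, and shortens only for patients without a severe cycle 1 event. The times are minimums, and staff may keep a symptomatic patient longer. This supports the schedule as a reasonable choice. It does not explain why the driving precaution depends on sedation.

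The consent pages were not available either and may contain driving advice, so the point is about the 7.1.1 precaution only. Advice there would not correct that text.

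Three other stronger readings should be resisted:
- **Undercounted adverse events or a biased MTD.** Section 11.2 requires documentation from first dose to 30 days after the last, and the DLT definition in section 4 covers cycle 1 without reference to the observation period.
- **The step-down phrase as a hole in protection.** Read literally it is the more protective text. Cutting it to 2 h, or even 3 h, after infusion would shorten what it now covers.
- **Adding up uncovered hours over several infusions as a share of the window.** The share depends on whether the fully observed infusion time is counted, and it assumes every patient steps down. Clock hours are not risks in any case.

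**Conclusion.** The point holds as a cheap safety improvement. By the protocol's own statement, 1 h (cycle 1) or 2 h (cycle 2 on, for patients without a severe cycle 1 event) of the event window falls after required observation ends. The driving precaution does not cover syncope or seizure in that time. This assumes that the 3 h runs from the end of the infusion and that patients leave when required observation ends. For patients with a severe cycle 1 event no later duration is stated; the longer schedule is only implied.

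Confidence is high in the wording and the clock times. The clinical effect is unknown, because the available text gives no distribution of event times. The step-down phrase is an editorial error, secondary to the precaution.

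**What to change.** **Main change, 7.1.1 Precautions.** State that for at least 3 h after the end of every infusion, in every cycle and regardless of sedation, patients should not drive or undertake hazardous activity. Keep the sedation clause as an additional restriction, and carry the sentence into the patient instructions. Cost: 1 h without driving after release in cycle 1 and 2 h from cycle 2, with no new visit or procedure.

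**Editorial change, 7.1.1 Monitoring.** Describe the scheduled period correctly, as 2 h after infusion and 3.5 h in total. In the same sentence, keep the rule that any severe event occurring or reported within 3.5 h after a cycle 1 infusion blocks step-down, so that the correction removes no protection. The symptom and toxicity reviews already scheduled in section 8.1 on days 8 and 15 and on day 1 of cycle 2 can pick up such events after release. Cost: wording only.

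**For the sponsor to weigh, not required.** Observing to 4.5 h in total would cover the window on site. It would add 1 h at each of the 3 cycle 1 infusions (3 h per patient) and 2 h at any later infusion to which it was applied. Wherever observation still ends sooner, the driving sentence is needed.

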10.1.9. Warnings and Precautions

Methotrexate has been reported to cause fetal death and/or congenital anomalies. Therefore, it is not recommended for women of childbearing potential unless there is clear medical evidence that the benefits can be expected to outweigh the considered risks. If a woman becomes pregnant or suspects that she is pregnant

while participating in this study, she must inform the investigator immediately and must permanently discontinue study drug.

Methotrexate elimination is reduced in patients with impaired renal function, ascites, or pleural effusions. Such patients require especially careful monitoring for toxicity, and may require dose reduction or, in some cases, discontinuation of methotrexate administration.

Unexpectedly severe (sometimes fatal) bone marrow suppression, aplastic anemia, and gastrointestinal toxicity have been reported with concomitant administration of methotrexate (usually in high dosage) along with some nonsteroidal anti-inflammatory drugs (NSAIDs).

Methotrexate causes hepatotoxicity, fibrosis and cirrhosis, but generally only after prolonged use. Acutely, liver enzyme elevations are frequently seen. These are usually transient and asymptomatic and also do not appear predictive of subsequent hepatic disease. Liver biopsy after sustained use often shows histologic changes, and fibrosis and cirrhosis have been reported.

Methotrexate-induced lung disease, including acute or chronic interstitial pneumonitis, is a potentially dangerous lesion, which may occur acutely at any time during therapy and has been reported at low doses. It is not always fully reversible and fatalities have been reported. Pulmonary symptoms (especially a dry, nonproductive cough) may require interruption of treatment and careful investigation.

Diarrhea and ulcerative stomatitis require interruption of therapy: otherwise, hemorrhagic enteritis and death from intestinal perforation may occur.

Like other cytotoxic drugs, methotrexate may induce "tumor lysis syndrome" in patients with rapidly growing leukemias. Appropriate supportive and pharmacologic measures may prevent or alleviate this complication.

Severe, occasionally fatal, skin reactions have been reported following single or multiple doses of methotrexate. Reactions have occurred within days of oral, intramuscular, intravenous, or intrathecal methotrexate administration. Recovery has been reported with discontinuation of therapy.

Potentially fatal opportunistic infections, especially *Pneumocystis carinii pneumonia*, may occur with methotrexate therapy.

11. Adverse Event Documentation and Reporting

Toxicity and adverse events will be classified according to NCI's Common Terminology Criteria for Adverse Events V 4.0. (CTCAE) and reported on the schedule below. A copy of the CTCAE can be downloaded from the CTEP home page

(http://ctep.cancer.gov/protocolDevelopment/electronic_applications/ctc.htm#ctc_40)

Note: throughout this section the generic term "drug" refers to 765IGF-MTX.

11.1. Definitions

The following definitions are based on the Code of Federal Regulations Title 21 Part 312.32 (21CFR312.32(a)).

Adverse Event: Any untoward medical occurrence associated with the use of a drug in humans, whether or not considered drug related.

Suspected Adverse Reaction: Any adverse event for which there is a reasonable possibility that the drug caused the adverse event.

Life-Threatening Adverse Event or Life-Threatening Suspected Adverse Reaction: An adverse event or suspected adverse reaction is considered “life-threatening” if, in the view of either the investigator or sponsor, its occurrence places the patient or subject at immediate risk of death.

Serious Adverse Event or Serious Suspected Adverse Reaction: An adverse event or suspected adverse reaction is considered “serious” if, in the view of either the investigator or sponsor, it results in any of the following outcomes:

- Death
- A life-threatening adverse event
- Inpatient hospitalization or prolongation of existing hospitalization
- A persistent or significant incapacity or substantial disruption of the ability to conduct normal life functions
- A congenital anomaly/birth defect.

Important medical events that may not result in death, be life-threatening, or require hospitalization may be considered serious when, based upon appropriate medical judgment, they may jeopardize the patient or subject and may require medical or surgical intervention to prevent one of the outcomes listed in this definition.

Preplanned hospitalization: A hospitalization planned before signing the ICF is not considered an SAE, but rather a therapeutic intervention. However, if during the preplanned hospitalization an event occurs, which prolongs the hospitalization or meets any other SAE criteria, the event will be considered an SAE. Surgeries or interventions that were under consideration, but not performed before signing the ICF, will not be considered serious if they are performed after signing the ICF for a condition that has not changed from its baseline level. Elective hospitalizations for social reasons, solely for the treatment of prior conditions or due to long travel distances are also not SAEs.

If either the IND sponsor or the investigator believes the event is life-threatening or serious, the event must be evaluated by the sponsor for expedited reporting (21CRF 312.32(a)).

Unexpected adverse event or unexpected suspected adverse reaction: An adverse event or suspected adverse reaction is considered “unexpected” if it is not listed in the investigator brochure or is not listed at the specificity or severity that has been observed; or, if an investigator brochure is not required or available, is not consistent with the risk information described in the general investigational plan or elsewhere in the current application, as amended. Thus, adverse events that occur as part of the disease process

or underlying medical conditions are considered *unexpected*; however, they will not be reportable per section 11.3.

Unanticipated (unexpected) problems/events defined as those that are *not* already described as potential risks in the consent form, are *not* listed in the Investigator's Brochure, and are *not caused by* an underlying disease.

Note: The major discord between the FDA and IRB definitions is whether or not the underlying disease is included when considering expectedness.

UPIRSO: Federal regulations [45CFR46.103(b)(5) and 21CFR56.108(b)(1)] require the IRB to ensure that researchers promptly report "any unanticipated problems involving risk to subjects or others" (UPIRSOs). The Mayo Clinic IRB defines a UPIRSO as any problem or event which in the opinion of the local researcher was unanticipated, reflects new or increased risk to the subjects and at least possibly related to the research procedures.

In addition, the Mayo Clinic IRB has defined the following problems/events as reportable using the Prompt Report form found on the IRB website:

- Any accidental or unintentional change to the IRB-approved protocol that increases risk or has the potential to recur
- Any deviation from the protocol taken without prior IRB review to eliminate apparent immediate hazard to a research subject
- Any publication in the literature, safety monitoring report (including Data and Safety Monitoring Reports), interim result or other finding that indicates an unexpected change to the risk/benefit ratio of the research
- Any breach in confidentiality that may involve risk to the subject or others
- Any complaint of a subject that cannot be resolved by the research staff
- Any other possibly related event which in the opinion of the investigator constitutes an unanticipated risk

Expedited (Rapid) Reporting: Certain events may require rapid notification to entities providing patient safety oversight (e.g. IRB, FDA) as detailed in section 11.3. For the IRB this is 5 working days. For studies under an IND, it is 7 or 15 calendar days.

